1. **Step 3 - Telephone Screening and Oral Consent:** After a waiting period of 10 days, patients who have not contacted the study recruitment center to opt out of the study are followed up by telephone. During the phone call, potentially eligible persons are asked if they are interested in participating in the study. We screen persons (both those contacted by us and those who reach out to us in response to the mailing) for eligibility using a set of prepared questions. Eligible patients who remain interested in the study are read the oral consent form. If the patient agrees to participate, the telephone baseline interview is completed. In cases where patient is unable to complete telephone baseline interview due to limited phone minutes, paper version of the baseline interview will be mailed to the patient with returned envelope. When the baseline data collection has been completed, patients are informed of the assignment group of their practice. If the recruitment goal has not been reached within a reasonable amount of time, we mail another batch of letters and repeat this process until the recruitment goal of an average of 63 participants per practice is met, or recruitment closes at the practice.
2. **A participant is considered enrolled in the study once they have completed the baseline survey.** In order for a participant to successfully complete the baseline survey they must complete the PAM, PHQ, PROMIS Global scale, adverse events questions, and demographics questions. The eligibility BP measurement will be the participant's baseline BP measurement in both arms. Consented participants in both arms will continue to attend their typical schedule of primary care appointments. We do not require a specific frequency of primary care visits during the study period.
3. **Step 4 – First Intervention Visit for Patients in CC/Stepped Care Practices Only:** The First Intervention Visit is conducted by the Care Manager (CM) at the participant's primary care practice. The participant is invited to meet both the CM and CHW. BP, height and weight measurements will be taken by typical personnel and in a manner that follows the practice site's normal procedures. The participant receives and is trained on the use of the home blood pressure monitor.

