 - i. **EMR.** The EMR data will be used to select potential patients for recruitment, obtain contact information for recruitment, and to assess clinical outcomes on enrolled patients. Data will be extracted just prior to recruitment and, for those enrolled, at 6-month intervals for up to 30 months of follow-up. Data elements will include BP measures, lipid levels, HbA1c and glucose levels, and other clinical measures of interest to the research team. The EMR is a valuable source of data. First, ours is a pragmatic trial, and real-world treatment decisions are made using EMR data. This will improve the value of our findings for real-world implementation. Second, these data elements are routinely collected when patients visit their provider. However, a major limitation of this data source is that unlike data collected at scheduled study visits, EMR data are only available if a patient visits their provider. We will minimize this limitation by only recruiting patients that have seen their provider within the 6 months preceding recruitment. We hope this will result in a patient sample with more complete follow up data.
 - ii. **Care Manager, CHW and Specialist records.** The care managers, CHWs and specialists from the study's specialist core will maintain consistent records on each patient participant with whom they interact or whose case they review. The data collected includes both quantitative and qualitative data. This information is entered in a study database. For the care managers and CHWs, three and fifteen visits, respectively, will also be audio recorded and assessed for use of motivational interviewing strategies. These data will be used in assessing both clinical and patient-centered outcomes.
 - iii. **Telephone surveys.** Our trained staff of recruiter/interviewers complete an interview with each participant at baseline, 6-, 12-, 18-, and 24-months. These data will be used to

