assess patient-centered outcomes, including Patient Activation Measure (PAM-13), health-related quality of life, medication adherence, patient satisfaction, and patient reported adverse events. When assessing patient reported outcomes, one needs to ask patients directly about their experiences. The validated instruments (see response to IR-4 below) are designed to accurately gather information about each patient's experience as part of this study, and our analysis plan will allow us to assess how this changes over time. The limitations of using telephone surveys are the length of the surveys (each of the surveys takes between 45 and 90 minutes to complete) and survey fatigue on the part of the participant.

iv. **Claims data.**

- 2. Instruments to be used for provider/staff data collection:** We are using limited surveys of providers and staff involved directly in the intervention (CMA super-users, practice champions, system level leaders, care managers, and community health workers) to collect knowledge and attitudes. Attitudes surveys will be no longer than ~15 minutes in average length. Baseline is defined as the time of enrollment of patients at the practice where the respondent works. For the comparison arm, respondents will be the same except there are no Care Managers. System- and practice-level leadership surveys will assess attitudes toward the interventions. Baseline is defined as the time of enrollment.

We conducted short interviews with system-level leaders to assess system values prior to the active intervention and will conduct interviews with leaders after the active intervention is complete. We conduct exit interviews with CMs and CHWs departing from the study to learn more about their experiences executing the study protocol and administer CM and CHW characteristic surveys, within 12 months of the first CM visit and 6 months of the first CHW visit, to measure CM and CHW attributes. We also conducted 30-minute in-person or telephone directed interviews with CMs. The interview focuses on assessing CMs' involvement with the RICH LIFE subspecialist core as a CM on the project. The interviews will be conducted by two study team members. The interview will be audiotaped based on each CM's permission. Finally, there are frequent qualitative check-ins with CHWs and CMs to assess program utility and progress (based on the RE-AIM framework, described further below).

3. Instrument to be used for practice-level data collection

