Primary endpoint: The primary endpoint is 12 month follow-up. Analysis on the following outcomes will take place after 12 month follow-up data collection has been completed.

Primary outcomes

The primary clinical outcome of the RICH LIFE Project is the percent of patients with BP <140/90 at 12 months. The primary patient reported outcome is change from baseline in self-reported patient activation, measured by the Patient Activation Measure (PAM-13), at 12 months.

Secondary outcomes

The most important secondary clinical outcome is change from baseline in systolic BP at 12 months. Additional secondary clinical outcomes include: 1) change from baseline in diastolic BP at 12 months; 2) percent with BP <130/80 mm Hg and with BP <120/80 mm Hg at 12 months; 4) change from baseline in 10-year projected probability of a CVD event (global Framingham Risk Score) at 12 months; 5) mean change from baseline in total cholesterol, low-density lipoprotein cholesterol (LDL-C), and high-density lipoprotein (HDL) and change from baseline in the percent with controlled total cholesterol, LDL, and HDL at 12 months for all patients and for the subgroup with hyperlipidemia; and 6) mean change from baseline in hemoglobin A1c and change from baseline in the percent with hemoglobin A1c < 7.0 at 12 months in patients with a diagnosis of diabetes.

Patient-reported secondary outcomes include: 1) attainment of self-determined goals related to self-management behaviors (e.g., medication adherence, healthy diet, physical activity, and smoking cessation);

2) medication adherence; 3) health related quality of life; 4) depressive symptoms; 5) patient assessment of care for chronic conditions; 6) patient ratings of trust in their care teams; and 7) hypertension knowledge and attitudes. We will compare change from baseline to 12 months to determine the effect of the intervention.

Secondary endpoint and outcomes

We will assess the following outcomes after 24 month follow-up is completed to determine the durability or “late” intervention effect: 1) the percent of patients with BP <140/90 at 24 months; 2) change from baseline in self-reported patient activation, measured by the Patient Activation Measure (PAM-13), at 24 months; 3) change from baseline in systolic and diastolic BP at 24 months. We will also compare the change from 12 months to 24 months.

Table 14 lists study measures, data sources, and collection time points.

Statistical analysis plan

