For the CC/Stepped Care arm, exploratory analysis will be conducted to determine which parts of the intervention, e.g., number of CM and CHW contacts, were more successful in improving BP control and reducing systolic BP, or if there was an overall “dose” effect.

Power calculation

We aim to recruit a total of $n=1,890$ unique patients. We planned for 20% random attrition which would yield an analytic sample of 1,500 (effective size of 50 patients per practice).^{104,105} A review of cluster-randomized trials in primary care found a median intracluster correlation coefficient (ICC) of 0.04, with an interquartile range of -0.02 to 0.21.¹⁶⁴ Assuming a 5% ICC, 15 clusters of 50 patients per intervention arm and a two-sided alpha of 0.05, we will have 80% power to detect a difference in proportion of patients with BP controlled of 11-13% (depending on whether the proportion controlled in the SCP arm is 50%-70%). With the same assumptions and sample size, using a two-sample t-test, we will be able to detect an effect size of 0.278. Operationalizing this for the primary and important secondary outcomes, we anticipate that for PAM-13, estimating a $SD=10.0$,¹⁶⁵ we would be able to detect a mean difference of 2.78 between the CC/Stepped Care and SCP arms; for systolic BP, estimating a $SD=19.5$ mm Hg,¹⁵³ we could detect a mean difference of 5.42 mm Hg between the CC/Stepped Care and SCP arms.

Design Considerations:

Participants will be considered to be enrolled at the time they are given their randomization assignment, which will occur at the end of the baseline interview. Data from all enrolled participants will be analyzed as intent-to-treat.

Missing Data

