6. *Consent for Trial Participants:* Trained recruiters at a study coordinating center will contact potential participants by telephone after 10 days from mailing of recruitment packet, to assess their willingness to participate in the study and complete eligibility screening and a baseline telephone questionnaire using a standardized telephone script and oral consent process. Patients will be told if they enroll in the study, we

will obtain data from their EMR and insurance claims for the purpose of monitoring their BP and other associated medical conditions (i.e. diabetes, hyperlipidemia, coronary heart disease, smoking status, and depression). They will also be informed that we will be asking them to complete several questionnaires via telephone interview at baseline, 6, 12, 18, and 24 months to obtain information about factors associated with their HTN and other conditions, as well as their experience in the clinical programs being tested in the trial. CMs and CHWs also ask patients to provide either written or oral consent (in the case of telephone encounters) before audio-recording patient encounters.

iii. **Protection Against Risk: Risks and Benefits:**

1. *Kick-Off/Town Hall Meetings:* The major risks for town hall meeting participants include loss of privacy or confidentiality. Meeting attendees are told they may refuse participation at any point in the study period. While meeting participants may not experience direct benefits, we inform participants that their engagement in the research process is part of a deliberate effort to improve patient care in primary settings and reduce disparity in healthcare access and outcomes.

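### PAM-13, a primary outcome, is collected by the same interviewer pool whose baseline calls end with disclosure of the practice's arm, and the protocol states no masking of follow-up interviewers

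*Combined protocol and SAP*

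**What the plan says.** Section 8 (Primary outcomes) states: "The primary patient reported outcome is change from baseline in self-reported patient activation, measured by the Patient Activation Measure (PAM-13), at 12 months". The scores come from the telephone surveys of Section 7B.1.iii: "Our trained staff of recruiter/interviewers complete an interview with each participant", at baseline and at 6, 12, 18 and 24 months.

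The baseline call belongs to the same staff. Under Risks to Human Subjects (consent for trial participants), "Trained recruiters at a study coordinating center will contact potential participants by telephone", and these recruiters carry out screening, oral consent and the baseline questionnaire. Section 5E, Step 3 adds: "When the baseline data collection has been completed, patients are informed of the assignment group of their practice". Section 8 (Design Considerations) places that step within the call, since participants count as enrolled when "they are given their randomization assignment, which will occur at the end of the baseline interview".

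The stated protection is that the patient finishes the baseline survey before learning the arm (Section 5E, Step 3; Risks to Human Subjects, randomized trial). Section 7C.4 assigns follow-up interviews to study staff by telephone, with mailed forms for patients short of phone minutes, and is silent on awareness of arm. The interviewer-training text in Section 8 (Missing Data) concerns complete answers and retention. The only blinding term found in the documents is the un-blinded statistician in Section 9C.

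**The concern.** PAM-13 is a subjective scale read out over the telephone. An interviewer who knows the arm can affect answers through prompting, tone or clarification, in the direction the study hopes for. Patients know their own arm, and that source of bias cannot be removed here. Interviewer influence is an additional source, and it can be reduced.

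The cluster design makes leakage easier. There are 30 practices averaging 63 patients, and arm is fixed by practice, so an interviewer who has closed one baseline call at a practice knows the arm for all its patients.

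Section 7A defends taking blood pressure from the EMR partly because this avoids bias from contact with researchers. PAM-13 depends on such contact (apart from mailed forms) and receives no comparable protection or acknowledgement. The planned sensitivity analyses address missing data, not measurement bias.

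**Working it through.** **Who knows what, and when**

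| Step | Protocol location | What is stated |
|---|---|---|
| Baseline PAM-13 | Section 5E, Steps 3 and enrolment definition | Collected before the patient is told the arm |
| Disclosure | Section 5E, Step 3; Section 8, Design Considerations | At the end of the baseline interview; the person disclosing is not named |
| 12-month PAM-13 | Section 7B.1.iii; Section 7C.4 | Same staff group, by telephone; awareness of arm not addressed |
| Free-text CM/CHW questions | Section 9B.b | Already placed at the end of the 12- and 24-month surveys |
| Other items for CC/Stepped Care only (ratings of the intervention, usefulness of the CHW) | Section 3E; Table 13 | Position relative to PAM-13 not stated |

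The protection therefore covers the patient at baseline. It does not cover the interviewer at 12 or 24 months.

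**The plan's own detectable difference** (inputs from Section 8, Power calculation: 15 clusters of 50 per arm, ICC 0.05, two-sided alpha 0.05, 80% power, PAM-13 SD 10.0)

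- Design effect = 1 + (50 − 1) × 0.05 = 3.45.
- Effective n per arm = (15 × 50) / 3.45 = 750 / 3.45 = 217.4.
- Standard error = √(2 / 217.4) = 0.0959 SD, or 0.96 PAM points.
- The noncentral t with 30 − 2 = 28 df gives 0.2784 SD at 80% power, which is 2.78 points. The plan's 0.278 and 2.78 are reproduced. A normal approximation would give 0.269.

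**Illustration of the stakes.** The bias sizes below are assumptions; no figure in the documents bears on them. If interviewers shift scores by an average of a in CC/Stepped Care and b in SCP, the arm contrast is biased by a − b. A shift common to both arms cancels. With no true effect, a net bias of d points gives a noncentrality of d / 0.96 on 28 df:

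| Assumed net bias (points) | Share of 2.78 | Two-sided rejection rate at nominal 5% |
|---|---|---|
| 0.5 | 0.5 / 2.78 = 18% | about 8% |
| 1.0 | 1.0 / 2.78 = 36% | about 17% |

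**The case against.** Several points on the other side stand.

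- **Same team, not same person.** A reader might infer that whoever disclosed a patient's arm also makes that patient's 12-month call. The documents do not show this. Disclosure is described in the passive, and follow-up is variously attributed to study staff, the study call center and data collectors. Nothing says that the call list displays the arm.
- **Order of questions.** A reader might infer that the CM/CHW questions reveal the arm before PAM-13 is asked. For the free-text questions the protocol points the other way, since they close the survey. Only the position of the other CC-only items is open.
- **Silence is not proof of absence.** The Manual of Procedures mentioned in Section 9 is not among the documents and may contain masking rules. If it does, citing them settles the point.
- **Limited gain.** Patients know their arm and rate themselves. Any mention of a care manager or CHW during the call, or at the earlier 6-month call, unmasks the interviewer. Some follow-ups are on paper with no interviewer.
- **Timing.** The protocol carries an October 2021 date. Section 6C (Coaching Calls) has all interventions in place by April 2019. Section 5E estimates seven months to enroll, starting one month before the other interventions begin. On those figures enrollment would end around October 2019 and the six-month calling window after the 12-month date around April 2021. Most or all 12-month calls were therefore probably complete, although Section 7C.3 still refers to about 588 participants without completed 24-month follow-up.

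These points narrow the concern and limit the remedy. They do not remove the gap: the protocol relies on an interviewer-administered primary outcome and does not say whether the follow-up interviewer is masked.

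**Conclusion.** The point holds as a modest, inexpensive improvement. A single interviewer pool collects PAM-13 at every survey, its baseline calls end with disclosure of a practice-level assignment, and the protocol describes no masking of follow-up interviewers.

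The size of any bias is not estimable from the documents. The 18% to 36% range follows only from an assumed net bias of 0.5 to 1.0 points, and only an effect that differs by arm would matter. It would be wrong to conclude that the PAM-13 comparison is biased by that amount, or at all. The documents show an opportunity for interviewer influence, not its occurrence. The conclusion also assumes that the Manual of Procedures contains no masking rule.

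**What to change.** For follow-up calls still to be made:

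1. Suppress both arm and practice in the REDCap call list and the weekly follow-up priority reports. Hiding arm alone is not enough, because practice identifies it.
2. Where feasible, route the call to an interviewer who did not do that patient's baseline call, without reducing the minimum of six call attempts.
3. Administer PAM-13 before every item that applies only to CC/Stepped Care.
4. Have the interviewer record whether the arm was known before PAM-13 was completed, and use this in a sensitivity analysis.

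For calls already made, report whether interviewers were masked (citing the Manual of Procedures if it covers this) and, if not, state it as a limitation of the PAM-13 result.

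The cost is a change to REDCap views and survey order, one extra data item, and slightly less flexible call scheduling. The documents do not give the team's size, so routing should remain a preference rather than a rule. Some patients will still reveal their arm, and respondent bias is not removed.

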The real-world distribution of race and ethnicity of patients varies across practices as a function of the residents of neighborhoods from which the practices draw. Although we continue to attempt to recruit up to 21 non-Hispanic white, non-Hispanic African-American, and Hispanic eligible patients at each practice, we acknowledge this variation and are aware that in some practices we will not be able to meet the recruitment goals for each race or ethnicity. In order to approach a somewhat balanced distribution in the overall analytic sample, we will oversample non-Hispanic African Americans in practices with high percentages of African-American patients and Hispanic patients in practices with high percentages of Hispanic patients. In turn, there are practices with percentages of whites so low that we are unlikely

to reach 21 participants. We have already de facto oversampled non-Hispanic whites in several practices because of low numbers of eligible participants in the other two targeted racial and ethnic groups.

We do not know the exact racial and ethnic distribution of patients eligible for our study until we receive recruitment data for each practice. Thus, to date, we have not able to predetermine a race/ethnicity oversampling plan. As additional practices join the study, however, we will over-recruit among Hispanics to increase balance among the three groups at the overall sample level. This will require that we recruit additional Hispanic hypertensive patients at the remaining 20 practices. It should be noted that these additional patients will be recruited in lieu of white patients in order to keep the average number of patients at CC/Stepped care practices at close to 63 (for care management purposes). It is our goal to obtain a sample of sufficient size to analyze Hispanics separately; however, the group size may ultimately be limited to 10% of the overall sample.

With respect to balance across intervention arms, we may face greater challenges reaching goals for Hispanic patients due to allocation of practices through randomization.

[figure not shown]
E. Participant Screening and Consent:

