We will use descriptive statistics to characterize the organizations, providers, and patients, using means and standard deviations, medians and interquartile ranges, or frequencies and percentages where appropriate. Descriptive statistics of central tendency and variability will be generated for outcomes. The distributions of each continuous outcome variable will be assessed for normality, and appropriate transformations will be made if necessary. Two-sample t-tests, Wilcoxon rank-sum tests, and Fisher’s exact test will be used to compare baseline demographic and practice characteristics across intervention arms.

Primary statistical analyses testing the differences in outcome (or change in outcome over time) between intervention groups will be conducted using the intention-to-treat principle. For our clinical outcomes at our primary endpoint of 12 month follow-up, we will select the EMR measure that is closest to 12 months following the baseline survey (enrollment date) for each patient as long as it is within the 6 month window.

General Approach

These analyses will utilize all available data through modeling approaches for correlated outcomes. All missing data will be assumed to be missing at random (MAR) conditioning on the observed data, and models will be adjusted for characteristics associated with missingness and key variables not balanced by the cluster randomization. In sensitivity analyses, missing data will be imputed using likelihood based longitudinal models developed under the MAR assumption. Missing data under plausible informative missing scenarios will be multiple-imputed using these likelihood based models with the mean models tuned according to the plausible informative missing scenarios. These sensitivity analyses will verify the robustness of the results derived under MAR assumption. All tests will be two-sided and significance will be set at $\alpha < 0.05$. Analyses will be conducted using SAS version 9.4 or higher (SAS Institute, Inc., Cary, NC) or Stata SE14 or higher (StataCorp, College Station, TX).

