We will use mixed-effects regression models for continuous outcomes and Generalized Estimating Equations (GEE) analysis for dichotomous outcomes. For mixed-effects regression modeling, we will assume an unstructured correlation structure for longitudinal analyses of outcomes with repeated measurements over time, employ random effects to address clustering by practices, include appropriate covariate adjustment in the fixed effects, and use robust estimates for statistical inferences. The GEE approach is robust to outcome correlation misspecification, so we will just assume an exchangeable correlation structure for the outcomes, include appropriate covariates in the mean model, and use robust estimates for statistical inferences. We will use mixed-effects regression models under the MAR assumption as the basis to conduct multiple imputation for missing BP data or other outcomes as appropriate. In sensitivity analyses evaluating potential impacts under sensible informative missing

(NMAR) scenarios, we will preserve the mixed-effects regression based variance-covariance estimates, and manipulate the mean model under each informative missing scenario to carry out multiple imputation. Missing binary outcomes (e.g., controlled BP or lipids) will be derived based on multiple-imputed continuous values using appropriate observed data likelihood models as described.

Statistical analysis plan for primary outcomes

For the primary clinical outcome of BP control at 12 months we will model the binary variable BP controlled (yes/no) at 12 months using GEE with a logit link on the intervention arm indicator (CC/Stepped Care arm vs. SCP arm). Additional covariates will be included as appropriate as described previously, including appropriate cluster level characteristics and variables associated with occurrence of missing data. With correctly specified mean model, the GEE is robust to misspecification of correlation structure so the statistical inferences will account for outcome correlation due to patients clustering within practice and be valid under MCAR. The regression coefficient for the intervention arm indicator estimates the log-odds ratio of BP control at 12 months for the CC/Stepped Care arm to the SCP arm. Multiple imputation of missing BP outcomes will be carried out to impute the missing BP control outcomes to produce proper inferences under MAR and to conduct sensitive analyses under NMAR scenarios.

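### Patient-level baseline tests ignore practice clustering, so their p-values tend to be too small for any characteristic that clusters by practice

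*Combined protocol and SAP*

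**What the plan says.** In Section 8, the opening of the statistical analysis plan names two-sample t-tests, Wilcoxon rank-sum tests and a Fisher test for the baseline table. Fisher's "exact test will be used to compare baseline demographic and practice characteristics across intervention arms". No allowance for clustering is attached to any of the three. Under General Approach, "All tests will be two-sided and significance will be set at" the 0.05 level.

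The same subsection sets the covariate rule: "models will be adjusted for characteristics associated with missingness and key variables not balanced by the cluster randomization". For BP control, the plan for the primary outcomes adds covariates "including appropriate cluster level characteristics and variables associated with occurrence of missing data". It gives no definition of imbalance and no covariate list.

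Elsewhere the plan treats patients within a practice as correlated. The power calculation reads "Assuming a 5% ICC, 15 clusters of 50 patients per intervention arm and a two-sided alpha of 0.05". The outcome models use GEE with robust inference or a practice random effect. The Randomization Scheme paragraph says that practices were allocated within blocks, stratified by practice network.

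**The concern.** The three named tests take the patient as the independent unit, whereas the practice was the unit allocated. When a characteristic clusters by practice, chance allocation of 30 practices moves the arm means or percentages further apart than these tests expect. Too many p-values then fall below 0.05.

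Two things are at stake. The first is the baseline table, which could suggest that randomisation failed when it did not. The second is covariate choice. The plan adjusts for key variables that are not balanced, and the only comparisons of baseline variables between arms that it describes are these tests. An analyst could reasonably take p < 0.05 as the criterion, and covariates would then enter the primary models through a test of the wrong size.

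**Working it through.** **Inputs from the documents.** 30 practices, 15 per arm; on average 63 patients per practice at enrolment (study population and recruitment sections); 50 per practice after 20% attrition, ICC 0.05 and two-sided 0.05 (Power calculation). The same paragraph cites primary-care ICCs with median 0.04 and interquartile range -0.02 to 0.21. No ICC is given for any baseline variable.

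**Step 1: reproduce the plan's own figure.** The design effect at follow-up is 1 + (50 - 1) × 0.05 = 3.45. The effective size per arm is 15 × 50 / 3.45 = 217.4. A noncentral t with 30 - 2 = 28 degrees of freedom gives a detectable effect of 0.278 SD at 80% power, as stated. For BP control, the detectable differences are 13.3, 12.7 and 11.5 points at comparator rates of 50%, 60% and 70%, which agrees with the stated 11-13%. The power calculation therefore does allow for clustering.

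**Step 2: true size of an unadjusted 5% baseline test.** Baseline tests use all enrolled patients, so m = 63. With simple 1:1 allocation of practices of equal size:

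- design effect D = 1 + 62 × ICC
- false-flag rate = 2 × [1 - Φ(1.96 / √D)]

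| ICC | D | False-flag rate |
|---|---|---|
| 0 | 1.00 | 5.0% |
| 0.01 | 1.62 | 12.4% |
| 0.04 | 3.48 | 29.3% |
| 0.05 | 4.10 | 33.3% |
| 0.10 | 7.20 | 46.5% |
| 0.21 | 14.02 | 60.1% |

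For ICC 0.05: √4.10 = 2.025, 1.96 / 2.025 = 0.968, and the two-sided tail area is 0.333. At an ICC of zero or below, the rate is 5% or less.

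**Step 3: check by simulation at ICC 0.05** (30 practices of 63). The t-test rejected in 32.9% of runs, Fisher's test in 32-33% and the rank-sum test in 31-34%. A t-test on the 30 practice means rejected in 4.7%, and stayed between 4.7% and 5.4% for ICCs from 0 to 0.21.

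**Step 4: allow for the stratified allocation.** Balancing arms within networks removes the between-network part of the variation. The documents do not say how between-practice variance divides, so this step rests on assumptions: networks of 11, 6, 5, 4 and 4 practices, ICC 0.05, and 25%, 50% or 75% of between-practice variance lying between networks. The unadjusted t-test then rejected in 29%, 23% and 15% of runs.

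**Step 5: practice characteristics.** Here each practice contributes one value, so n = 30 is the right unit and the named tests are not inflated.

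**The case against.** The strongest reply is that this concerns a descriptive table. The primary analyses account for clustering through GEE with robust inference and a practice random effect, so the baseline tests do not disturb their standard errors. That stands.

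Three stronger readings are tempting, and the documents do not support them.

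- **That a third of patient variables will look imbalanced.** The 5% ICC is a planning value for outcomes. The cited interquartile range spans false-flag rates from about 5% to 60%, and stratification by network pulls the rate down. Unequal practice sizes, which Section 5 expects, tend to push it up.
- **That imbalance, judged by these p-values, decides the covariates.** Imbalance is one stated route, limited to key variables, beside predictors of missingness and cluster-level characteristics. Nothing in the text ties it to the p-values; that link is an inference from the absence of another criterion.
- **That race and ethnicity must be the worst case.** Section 5D says "The real-world distribution of race and ethnicity of patients varies across practices", and it plans oversampling of African-American and Hispanic patients where they are most numerous, which would raise clustering. It also aims for up to 21 patients per group at each practice and starts recruitment with the least represented group, which would lower it. The net ICC is unknown.

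A flagged variable would also differ in the sample. What an unadjusted p-value cannot support is the claim that the difference exceeds what chance allocation of practices produces. Adjusting for a prognostic variable that differs by chance is legitimate in itself.

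**Conclusion.** The point holds in a conditional form. As written, the plan prescribes patient-level tests of the wrong size for any baseline characteristic that clusters by practice. At ICC 0.05 with 63 per practice, the nominal 5% becomes about 33% under simple allocation and about 15-29% under the assumed network structure. Even the lowest of these is three times nominal. The rate could be near 5% for a variable that hardly clusters and about 60% at ICC 0.21. *Balanced* here means balanced in expectation.

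The demonstrated harm is a misleading baseline table. The effect on covariate choice is possible but inferred, and no effect on the primary estimate has been shown. A reader might conclude that the primary result is invalid; the planned handling of clustering in the outcome models does not support that. The stated analysis is nevertheless wrong for the design and cheap to correct.

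**What to change.** 1. Remove the patient-level baseline tests. Report means, medians or percentages by arm with standardised differences.
2. If a p-value is wanted for a patient characteristic, take it from a model with a practice random effect or from a comparison of practice means. Under the stratified scenarios in Step 4, a plain t-test on practice means rejected in only 1.0-3.1% of runs, so it errs on the cautious side.
3. State that baseline p-values do not select covariates.
4. Name the adjustment covariates in advance, for example practice network and the baseline outcome value where it applies. The PAM-13 and continuous BP models already carry baseline as a repeated measure, so this matters mainly for the BP control model. Without this list, dropping the p-values would still leave covariate choice open after the baseline data are seen.

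Tests on practice characteristics can stay. The cost is a few sentences of SAP wording; no new data are needed.
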